Thus, 44 patients each will be randomized to the placebo and IX-01 400 mg dose groups, and 66 patients each will be randomized to the IX-01 800 mg and IX-01 1200 mg dose groups. The 2:3 ratio results in only slight loss of statistical power from 1:1 randomization while increasing the chances that a patient will be randomized to an effective dose of study drug.

Assuming an alpha (2-sided) of 0.05 and an SD of 70 seconds, a sample size of 220 patients randomized in total (44 to the placebo and IX-01 400 mg dose groups and 66 to the IX-01 800 mg and IX-01 1200 mg dose groups) provides approximately 85%, 90%, and 90% power to detect a mean difference of 45 seconds between change from baseline in geometric mean (GM) of IELT for the IX-01 400 mg, IX-01 800 mg, and IX-01 1200 mg dose groups, respectively, compared with the placebo group.

Sequential multiplicity control testing of IX-01 1200 mg dose versus placebo, followed by IX-01 800 mg dose versus placebo and then IX-01 400 mg dose versus placebo will be done in order to control for multiplicity.

Additional patients may be recruited if some patients discontinue from the study with less than 2 postbaseline IELT assessments.

Statistical Methods:

The primary efficacy endpoint of this study is the change in GM IELT over the treatment assessment period compared with baseline, ie, $[GM(IELT_{\text{treatment period}}) - GM(IELT_{\text{baseline}})]$.

Change from baseline in GM IELT over the treatment assessment period will be analyzed using a mixed linear model, including treatment and baseline IELT as fixed factors and site

as a random factor.

The primary comparison of interest is IX-01 1200 mg versus placebo. If it is statistically significant at $\alpha=0.05$, then the following comparisons will be tested in the following order:

- IX-01 800 mg vs placebo group
- IX-01 400 mg vs placebo group

If at any point in the sequence statistical significance is not met, then subsequent analyses in the sequence cannot be deemed statistically significant. In such cases, nominal *P* values and 95% CI will be reported and interpreted in an exploratory manner. Irrespective of whether there are any statistically significant differences between treatment groups, IELT data from all treatment groups will also be used to model a possible dose response relationship.

The same approach to control for multiple comparisons as proposed for the primary endpoint will be used for each secondary endpoint analysis.

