The following key secondary efficacy endpoints will be analyzed:

1. Fold change in GM IELT over the treatment assessment period compared with baseline.
2. Proportion of patients with ≥ 2.5 -fold increase in GM IELT over the treatment assessment period compared with baseline, ie, [proportion of subjects with $\text{GM}(\text{IELT}_{\text{treatment period}})/\text{GM}(\text{IELT}_{\text{baseline}}) \geq 2.5$].
3. Proportion of patients rating their PE as improved per the CGIC questionnaire.
4. Proportion of patients achieving mean change in category of ≥ 1 or ≥ 2 on control of timing of ejaculation (PEP), ie, improving control from “very poor” or “poor” to “fair,” “good,” or “very good” at end of treatment.
5. Proportion of patients achieving mean change in category of ≥ 1 or ≥ 2 in ejaculation-related personal distress (PEP), ie, improving rating of ejaculation-related distress to “moderate,” “a bit,” or “not at all” at end of treatment.
6. Proportions of patients achieving change in category of ≥ 2 on control of timing of ejaculation (PEP) and achieving change in category of ≥ 1 in ejaculation-related personal distress (PEP) at end of treatment.

7. Mean change from baseline in score on control of ejaculation (e-diary) over the treatment assessment period.
8. Mean change from baseline in score on ejaculation-related personal distress (e-diary) over the treatment assessment period.

Analyses of e-diary data expressed in change from baseline over the treatment assessment period will be carried out using a mixed linear model. All analyses should include treatment, baseline IELT, and the baseline score of the analyzed endpoint as fixed effects and the site as a random effect.

For each analysis on proportion endpoints, difference in the proportions between each test group and placebo group will be tested using a logistic model. All analyses should include treatment, baseline IELT and the site as factors. *P* values and adjusted odds ratios will be presented.

Amendment 1.0:

16 January 2017

List of Abbreviations

Abbreviation	Definition
AE	Adverse event
ALT	Alanine aminotransferase
AST	Aspartate aminotransferase
BMI	Body mass index
CGIC	Clinical Global Impression of Change
CNS	Central nervous system
CRF	Case report form
C-SSRS	Columbia-Suicide Severity Rating Scale
CYP3A4	Cytochrome P450 3A4
DSM-IV	Diagnostic and Statistical Manual of Mental Disorders, Fourth Edition
ECG	Electrocardiogram
eCRF	Electronic case report form
EDC	Electronic data capture

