7.6 Statistical Analysis Methodology

Summary statistics will be provided for all study endpoints. For continuous endpoints n (number of patients included in the analysis), mean, SD, median, minimum, maximum, Quartile 1, and Quartile 3 will be provided. For categorical endpoints, the number and frequency in each category will be provided. Adjusted effect size and 95% CI will be displayed for all treatment comparisons.

For the purpose of e-diary data analyses, the treatment assessment period will include all assessments done between end of treatment and end of treatment minus 28 days, if patients have a sufficient amount of assessments within this time window. The time window may be extended back for patients without a sufficient amount of assessments within the predefined time window. Additional details will be provided in the SAP regarding the derivation of the treatment assessment period.

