7.6.1 Analysis of Primary Efficacy Endpoint

[figure not shown]
The primary efficacy analysis of the primary endpoint will be performed on the mITT population. Change from baseline in GM IELT over the treatment assessment period will be analyzed using a mixed linear model, including treatment and baseline IELT as fixed factors and type of site as a random factor.

The primary comparison of interest is IX-01 1200 mg versus placebo. If it is statistically significant at $\alpha=0.05$, then the following comparisons will be tested in the following order:

- IX-01 800 mg vs placebo group
- IX-01 400 mg vs placebo group

An overview of the approach to control for multiple comparisons is provided in Figure 7-1.

Figure 7-1 Overview of the Multiplicity Control

If at any point in the sequence statistical significance is not met, then subsequent analyses in the sequence cannot be deemed statistically significant. In such cases, nominal P values and 95% CI will be reported and interpreted in an exploratory manner. Irrespective of whether there are any statistically significant differences between treatment groups, IELT data from all treatment groups will also be used to model a possible dose response relationship. Further details on dose response analysis will be provided in the SAP.

The analyses above will be repeated using the Per-Protocol and ITT populations to examine the robustness of the primary results.

As a sensitivity analysis of the primary endpoint, a nonparametric approach will be carried out on the mITT population in order to obtain the median treatment effect and 95% CI.

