7.6.2.1 Change From Baseline Endpoints

Analyses of e-diary data expressed in change from baseline over the treatment assessment period will be carried out using a mixed linear model. All analyses should include treatment, baseline IELT, and the baseline score of the analyzed endpoint as fixed effects and the site as a random effect. In addition to the mixed linear model, a nonparametric approach may be carried out for specific secondary endpoints. Further details will be provided in the SAP.

Change in score from baseline in each of the PEP questions (ie, Endpoint 17 of Section 7.2.2) will be carried out using a mixed-effect model repeated measure model. All analyses should include treatment, baseline IELT, the baseline score of the analyzed endpoint, the visit, and the interaction between visit and treatment as fixed effects and the site as a random effect. Visit will be considered as the repeated measurement.

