7.6.2.2 Proportion Endpoints

For each analysis on proportion endpoint, difference in the proportions between each test group and placebo group will be tested using a logistic model. All analyses should include treatment, baseline IELT, and the type of site as factors. *P* values and adjusted odds ratios will be presented.

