7.6.2.3 Percentage Endpoints

The percentage of intercourse attempts lasting longer than a predefined threshold during the treatment assessment period will be analyzed by treatment as continuous data.

Analyses will be carried out using a mixed linear model. All analyses should include treatment and baseline IELT as fixed effects and the type of site as a random effect.

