13.4 Appendix 4 Amendment 1.0

Reasons for Amendment

- Inclusion of new data from recently complete caplet bioavailability study IX-0106
- 1600 mg dose changed to 1200 mg dose thus number of caplets required per single dose reduced from four caplets to three caplets
- Inclusion of additional information to be collected in LogPad as suggested by FDA

Protocol Sections Amended

The amended protocol sections are detailed below. The format is as follows:

- The “change from” section represents the current text in the protocol
- The “change to” section represents the revised text. Bolded text is used to indicate the addition of information to the current text, and strike-out text (e.g. ~~text~~) is used to show the deletion of information from the current text

Summary of Changes

All references to 1600 mg dose have been changed to 1200 mg throughout the protocol with the exception of pages 25 and 26 which refer to the 1600 mg dose in the Multiple-Ascending Dose Study (2)

All references to 4 caplets have been changed to 3 caplets throughout the protocol

All references to ‘type of site’ have been replaced with ‘site’ throughout the protocol

Protocol Synopsis

Efficacy Assessments

Change From

Patient Questionnaires/Instruments:

Questionnaires administered at the end of the run-in period and after 4 and 8 weeks of double-blind treatment

- Premature Ejaculation Profile (PEP)

Questionnaire to be administered at end of double-blind treatment only

- Clinical Global Impression of Change (CGIC)

Change To

Patient Questionnaires/Instruments:

Questionnaires administered at the end of the run-in period and after 4 and 8 weeks of double-blind treatment

- Premature Ejaculation Profile (PEP) **including additional question on bother**
- **Patient Global Impression of Severity (PGIS)**

Questionnaire to be administered at end of double-blind treatment only

- Clinical Global Impression of Change (CGIC)

List of Abbreviations

Add Text

PGIS Patient Global Impression of Severity

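### The site term has two names and only the logistic models do not call it random; coded as about 30 fixed levels, they would overstate the CGIC and distress odds ratios

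*Combined protocol and SAP*

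**What the plan says.** The current text describes the site term as follows.

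| Place | Model | Name of term | Called random? |
|---|---|---|---|
| Synopsis, Statistical Methods (primary) | mixed linear | site | yes |
| Synopsis (e-diary change scores) | mixed linear | site | yes |
| Synopsis (proportions) | logistic | site | **no** |
| 7.6.1 (primary) | mixed linear | type of site | yes |
| 7.6.2.1 (e-diary and PEP change scores) | mixed linear; repeated measures | site | yes |
| 7.6.2.2 (proportions) | logistic | type of site | **no** |
| 7.6.2.3 (percentage of attempts) | mixed linear | type of site | yes |

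The wording of the linear models is, in the synopsis, "mixed linear model, including treatment and baseline IELT as fixed factors and site" (the sentence goes on to call site random); in 7.6.1, "including treatment and baseline IELT as fixed factors and type of site as a random factor"; in 7.6.2.1, "and the baseline score of the analyzed endpoint as fixed effects and the site as a random effect"; and in 7.6.2.3, "the type of site as a random effect".

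The logistic text reads "All analyses should include treatment, baseline IELT, and the type of site as factors" in 7.6.2.2 and "All analyses should include treatment, baseline IELT and the site as factors" in the synopsis. These models supply P values and adjusted odds ratios for key secondary endpoints 2 to 6 and for the other responder endpoints. Section 7.6 adds: "Adjusted effect size and 95% CI will be displayed for all treatment comparisons". The plan expects about 30 sites and 220 randomized patients.

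**The concern.** There are two separate defects. First, a term that appears in three model statements is undefined, and the synopsis and body disagree about it for the same analyses. Second, the logistic text lists treatment, baseline IELT and site together as factors in a plain logistic model. A programmer working from the synopsis could reasonably enter site as a class variable with about 30 levels.

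That choice matters more in a logistic model than in a linear one. When many nuisance parameters are each estimated from a handful of binary outcomes, unpenalised maximum likelihood pushes the treatment odds ratio away from 1. Sites with all or no responders contribute nothing to it. At stake are the size of the reported odds ratios and the coverage of their intervals, in a dose-finding trial whose estimates may guide dose choice and later planning.

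**Working it through.** **The plan's own figure.** The plan gives no power or sample size for the proportion endpoints. Its primary-endpoint power reproduces by the normal approximation: 45 / (70 × √(1/44 + 1/44)) − 1.96 = 1.055, power 85.4%; and 45 / (70 × √(1/44 + 1/66)) − 1.96 = 1.343, power 91.0%. The plan states about 85%, 90% and 90%. This point does not touch those figures.

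**Inputs from the protocol.** About 30 sites (synopsis); 44/44/66/66 patients (Section 7.3); earlier-trial response rates, IX-01 against placebo, of 44% and 13% for CGIC and 46% and 16% for distress (Section 1.3.5).

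- Patients per site: 220/30 = 7.3; placebo patients per site: 44/30 = 1.5.
- True CGIC OR: (0.44/0.56)/(0.13/0.87) = 5.26.
- True distress OR: (0.46/0.54)/(0.16/0.84) = 4.47.
- Parameters with fixed sites: 30 site + 3 treatment + 1 baseline = 34, against about 80 expected CGIC responders (44 × 0.13 + 44 × 0.35 + 132 × 0.44 ≈ 79).

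**Assumptions not in the documents.** Site sizes equal, uneven (Dirichlet(3)) or very uneven (Dirichlet(1)); between-site SD 0, 0.3 or 0.6 and a baseline slope of 0.3 per SD, both on the logit scale; 800 and 1200 mg at the earlier active rate; 400 mg at 35-36%. Two endpoints × 3 enrolment patterns × 3 SDs = 18 settings, with 1,200 trials each. The comparison is 1200 mg against placebo.

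| Result over the 18 settings | Fixed site, ordinary ML | Random site intercept |
|---|---|---|
| Median OR, CGIC (true 5.26) | 6.5-7.4 | 5.3-5.7 |
| Median OR, distress (true 4.47) | 5.5-6.1 | 4.6-4.8 |
| Median log OR / true log OR | 1.129-1.204 | 1.007-1.047 |
| 95% CI coverage | 91-95% | 95-97% |

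As a check on the CGIC row, ln 6.5 / ln 5.26 = 1.872/1.660 = 1.13. The excess with fixed sites is 17-20% for equal site sizes, 15-17% for uneven and 13-14% for very uneven. The random intercept is itself 1-5% high, so 9-18 percentage points come from fixing site. The Monte Carlo SE of the ratios is about 0.013.

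**Dependence on the number of levels.** The excess is 13-14% with 25 sites, 12% with 20, 2-9% if sites with fewer than 8 patients are pooled, and −5% to +5% for a 2- or 4-level factor. Leaving site out gives −5% to +3%.

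**Null case.** Response rates of 13% and 30%, three enrolment patterns, SD 0.3 and 0.6, 2,500 trials each (30,000 in all), nominal 5%. Fixed-site Wald tests reject in 4.7-6.9% (mean 5.8%), random-intercept Wald tests in 3.4-5.2% (mean 4.3%). A likelihood ratio test, which the plan does not name, would reject in 5.6-9.0% (mean 7.0%) with fixed sites.

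**Second simulation.** Separate code, with site SD 0, 0.5 and 1.0 and graded dose effects, gave mean log ORs 20-24% too large with 30 equal fixed sites and 4-7% too large with a random intercept. Averaging on the log scale gives CGIC ORs of 7.6-7.9. The medians in the same runs were 7.25-7.49, so much of the gap from the table is mean against median.

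**Very low placebo response.** The earlier trial's control endpoint was 33% against 3%. The chance of no responder among 44 placebo patients is 0.97^44 = 26%, and then neither fit has a finite OR. In trials with at least one placebo responder, the log OR was about 7% too large with fixed sites and 5% too small with a random intercept.

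**The case against.** The bias needs four things at once: *site* rather than *type of site*, fixed effects, no pooling, and unpenalised likelihood. The plan states none of the last three. The word *factor* does not imply fixed, since 7.6.1 itself speaks of a random factor. Read literally, 7.6.2.2 might mean a few-level factor with almost no bias. All of this stands, so a reader may not conclude that the plan specifies fixed sites. It does not remove the defect: the synopsis wording most naturally becomes a class variable with about 30 levels, and nothing in the logistic text steers away from that.

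The two names are probably an editing leftover. The amendment summary says "All references to ‘type of site’ have been replaced with ‘site’ throughout the protocol", which shows that *site* is intended. That is accepted, and the log is used for intent only. The conflict lies in the current text and still has to be corrected.

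The shift is also modest beside the sampling error. Unadjusted, the CGIC log OR has SE √(1/5.72 + 1/38.28 + 1/29.04 + 1/36.96) = 0.51, so a 95% CI around 5.26 runs from about 1.9 to 14. The shift, ln(6.5/5.26) to ln(7.4/5.26), is 0.21 to 0.34, or roughly 0.4 to 0.7 SE. This is fair and limits the severity. But the error is systematic, always flatters an effective dose, and costs nothing to avoid.

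Finally, the rates come from one small trial with 3 and 4 placebo responders, and the site SD, slope and enrolment pattern are assumed. The direction and rough size held across all the assumptions tried at these two sets of rates; the exact percentage should not be relied on.

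**Conclusion.** The point holds in a conditional form. The site term is inconsistently named, and the logistic models leave its role open. Under the fixed, unpooled, ordinary maximum likelihood reading, the CGIC and distress odds ratios are materially overstated and their intervals cover somewhat too rarely. The size rests on about 30 sites, the earlier trial's rates and the assumed site variation.

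Four stronger conclusions might be inferred and are not supported:

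- *The primary analysis is biased.* Its site term is random in both places; only the name differs.
- *The tests are invalid.* At the null the Wald rejection rate averages about 5.8%, and with a real effect fixed sites reject slightly less often than a random intercept.
- *Every responder endpoint is inflated by 13-20%.* Only CGIC and distress rates gave that size. At 3% against 33% the excess was smaller and the main problem was an empty placebo cell.
- *The model would be chosen after unblinding.* Nothing shows this. The protocol sends much analysis detail to a SAP, and although 7.6.2.2 carries no such pointer of its own, its silence is not evidence of a late choice.

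The change should be made, but it concerns the estimates on secondary endpoints, not the trial's main conclusion.

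**What to change.** Replace *type of site* with *site* in 7.6.1, 7.6.2.2 and 7.6.2.3. In 7.6.2.2 and the synopsis, specify a logistic mixed model with treatment and baseline IELT as fixed effects and a random intercept for site, fitted by maximum likelihood with numerical quadrature. State that the same model is reported if the site variance is estimated as zero. Add a fallback, such as Firth-penalised logistic regression without site, for any endpoint where an arm has no responders or all responders. The fallback was not simulated.

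This matches the plan's linear models. A conditional logistic model or a pre-specified pooling rule would also settle the question. Omitting site is about as accurate in size, but it drops an adjustment the plan asks for and runs 3-5% low when sites differ (SD 0.6).

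The cost is wording in four places and standard software. The downsides are slightly less complete adjustment if sites differ strongly, and less favourable odds ratios. No power was lost in simulation: the random intercept rejected 0-2 percentage points more often than fixed sites.

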2.2 Secondary Objectives

- To determine the efficacy of three different dose levels of IX-01 on Clinical Global Impression of Change (CGIC), control of ejaculation, ejaculation-related distress and interpersonal difficulty, and satisfaction with sexual intercourse in men with PE.
- To determine the toleration and safety of three different dose levels of IX-01 taken as required in men with PE.

[figure not shown]
3 Investigational Plan

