4.1.2 Exclusion Criteria

1. Any IELT value > 2 minutes during the run-in period.
2. Any patient making < 4 attempts at sexual intercourse during the run-in period (screening may be extended or patient may be rescreened if there are extenuating circumstances).
3. Any patient who rates his control of ejaculation as fair, good, or very good (PEP question administered at the end of the run-in period).
4. Any patient who rates his ejaculation-related “personal distress” as “not at all” or “a little bit” (PEP question administered at the end of run-in period).

5. Coexisting Erectile Dysfunction (IIEF Erectile Function domain <22 during the run-in period).
6. Concomitant use of phosphodiesterase type 5 (PDE5) inhibitors, SSRIs/selective serotonin norepinephrine reuptake inhibitor (SSNRIs), monoamine oxidase inhibitors, alpha blockers, 5-alpha reductase inhibitors, topical anesthetics, and/or tramadol.
7. Any history (last 6 months) of use of Botox or similar product to treat PE.
8. Any patient who has received IX-01 in a previous clinical study.
9. Any patient who is unwilling to stop other treatments for PE (including but not limited to pharmacological, sex therapy, psychotherapy multiple condoms, and prior masturbation).
10. Any other sexual disorder of patient or partner that could interfere with results.
11. Any current sexually transmitted disease.
12. Any major medical condition of patient that could interfere with ability to have sexual activity and/or require hospital treatment.
13. Body mass index (BMI) >40 kg/m² or weight <60 kg.
14. Participation in a clinical drug study anytime during the 30 days prior to screening.
15. History of or positive test results for Human immunodeficiency virus (HIV), hepatitis B.
16. History of prostate disease or clinically significant prostate disease.
17. History of myocardial infarction, coronary bypass surgery, coronary artery angioplasty, unstable angina, clinically evident congestive heart failure, cardiac pacemaker, or cerebrovascular accident.
18. Cardiac arrhythmia: significant cardiac arrhythmia shown on screening ECG, or a known or suspected history of significant cardiac arrhythmias.
19. History of drug-induced allergic reactions including skin reactions.
20. History of congenital QT prolongation and/or corrected QT interval >450 msec at screening visit using the Bazett formula.

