7.2.2 Other Secondary Efficacy Endpoints

The following other secondary efficacy endpoints will be analyzed:

1. Fold change from baseline in (arithmetic) mean IELT over the treatment assessment period.
2. Change from baseline in (arithmetic) mean IELT over the treatment assessment period.
3. Proportion of patients with GM IELT of ≥ 1 minute over the treatment assessment period.
4. Proportion of patients with GM IELT of ≥ 2 minutes over the treatment assessment period.
5. Proportion of patients with GM IELT of ≥ 3 minutes over the treatment assessment period.
6. Proportion of patients with GM IELT of ≥ 4 minutes over the treatment assessment period.
7. Proportion of patients with GM IELT of ≥ 5 minutes over the treatment assessment period.
8. Proportion of patients with GM IELT increase over the treatment assessment period of ≥ 45 seconds compared with baseline.
9. Proportion of patients with GM IELT increase over the treatment assessment period of ≥ 1 minute compared with baseline.
10. Percentage of intercourse attempts lasting > 1 minute over the treatment assessment period.
11. Percentage of intercourse attempts lasting > 2 minutes over the treatment assessment period.
12. Percentage of intercourse attempts lasting > 3 minutes over the treatment assessment period.
13. Percentage of intercourse attempts lasting > 4 minutes over the treatment assessment period.
14. Percentage of intercourse attempts lasting > 5 minutes over the treatment assessment period.
15. Proportion of patients improving on PGIS
16. Proportion of patients achieving ≥ 1 category of improvement from baseline to end of treatment in each of the following (from 4-weekly PEP questionnaire):

- a. Satisfaction with sexual intercourse
 - b. Control over ejaculation during sexual intercourse
 - c. Ejaculation-related distress
 - d. Ejaculation-related interpersonal difficulty
 - e. Ejaculation-related bother
17. Change in score from baseline in each of the following (from 4-weekly PEP questionnaire):
- a. Satisfaction with sexual intercourse
 - b. Control over ejaculation during sexual intercourse
 - c. Ejaculation-related distress
 - d. Ejaculation-related interpersonal difficulty
 - e. Ejaculation-related bother

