7.3 Sample Size Calculations

The target total is for 220 patients to be randomized in the study.

The randomization ratio will be 2:2:3:3 (placebo, IX-01 400 mg, IX-01 800 mg, and IX-01 1200 mg dose groups, respectively).

Thus, 44 patients each will be randomized to placebo and IX-01 400 mg dose groups, and 66 patients each will be randomized to IX-01 800 mg and IX-01 1200 mg dose groups. The 2:3 ratio results in only slight loss of statistical power from 1:1 randomization, while increasing the chances that a patient will be randomized to an effective dose of study drug.

Assuming an alpha (2-sided) of 0.05 and an SD of 70 seconds, a sample size of 220 patients randomized in total (44 to the placebo and IX-01 400 mg dose groups and 66 to the IX-01 800 mg and IX-01 1200 mg dose groups) provides approximately 85%, 90%, and 90% power to detect a mean difference of 45 seconds between change from baseline in GM of IELT for the IX-01 400 mg, IX-01 800 mg, and IX-01 1200 mg dose groups, respectively, compared with the placebo group.

Sequential multiplicity control testing of IX-01 1200 mg dose versus placebo, followed by IX-01 800 mg dose versus placebo and then IX-01 400 mg dose versus placebo will be done in order to control for multiplicity. See details below.

Additional patients may be recruited if some patients discontinue from the study with less than 2 postbaseline IELT assessments.

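### The PEP and PGIS responder models omit the baseline category of the analysed item, at a modest, assumption-dependent cost in precision

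*Combined protocol and SAP*

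**What the plan says.** - **Responder model.** Section 7.6.2.2 prescribes a logistic model for every proportion endpoint: "All analyses should include treatment, baseline IELT, and the type of site as factors". The synopsis has site in place of type of site; the difference does not matter here. Neither names the baseline score of the item.
- **Change-score models.** Section 7.6.2.1 does include it. For e-diary changes: "All analyses should include treatment, baseline IELT, and the baseline score of the analyzed endpoint as fixed effects". The repeated-measures model for endpoint 17 (change in the five PEP items) also carries the baseline item score.
- **Endpoint 16.** Section 7.2.2 counts men with at least one "category of improvement from baseline to end of treatment in each of the following (from 4-weekly PEP questionnaire". The items are satisfaction, control, distress, interpersonal difficulty and bother. Appendix 2 scores each from 1 to 5, with 5 best.
- **Entry.** Section 4.1.2, exclusion 3, removes "Any patient who rates his control of ejaculation as fair, good, or very good", so baseline control is 1 or 2. Exclusion 4 limits baseline personal distress to 1 to 3. No PEP cut-off applies to the other three items.
- **Objective.** Section 2.2 covers "ejaculation-related distress and interpersonal difficulty, and satisfaction with sexual intercourse in men with PE". Bother is not named there, and section 6.2 calls that question exploratory.
- **Population.** Section 7.6.2 runs all secondary analyses on the ITT set.

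**The concern.** Two separate things are at work.

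First, the definition of endpoint 16 on the full ITT set makes a man who enters at category 5 a non-responder in any arm. For interpersonal difficulty and satisfaction nothing at entry prevents this. Such men pull all response rates toward zero and shrink the difference from placebo.

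Second, the logistic models ignore a strong candidate predictor of response. On key endpoint 4, read as reaching fair or better, a man at poor must move one category and a man at very poor two. Similar reasoning applies to endpoints 5 and 6 and to PGIS improvement. Chance imbalance in baseline category between arms of 44 and 66 then goes unadjusted.

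At stake are the power and precision of the responder comparisons. The plan gives no reason for adjusting the change in an item for its baseline but not the responder version of the same item.

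**Working it through.** **1. The plan's own power figure.** Section 7.3 gives the inputs ("Assuming an alpha (2-sided) of 0.05 and an SD of 70 seconds"), the arms ("44 to the placebo and IX-01 400 mg dose groups and 66 to the IX-01 800 mg and IX-01 1200 mg dose groups") and the result ("provides approximately 85%, 90%, and 90% power to detect a mean difference of 45 seconds between change from baseline in GM of IELT"). With power = Φ(45/(70·√(1/44 + 1/n)) − 1.960):
- n = 44: 45/14.92 = 3.015, power 85.4% (noncentral t: 84.7%).
- n = 66: 45/13.62 = 3.303, power 91.0% (noncentral t: 90.6%).

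The figure reproduces, but it concerns IELT. No power or expected rate is stated for the PEP responder endpoints.

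**2. Effect of men at category 5 on endpoint 16.** Let c be their share, which is not documented; I take 0 to 40% as an assumption. As an illustration, suppose that men able to improve respond as on the Phase 2a distress item in section 1.3.5: 46% on IX-01, 16% on placebo. Both rates are multiplied by (1 − c). Power for 44 versus 66 is Φ((Δ − 1.96·SE0)/SE1), where SE0 uses the pooled rate and SE1 the separate rates.

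At c = 40% the rates are 9.6% and 27.6%, and the pooled rate is (44×0.096 + 66×0.276)/110 = 0.204. SE0 = √(0.204×0.796×(1/44 + 1/66)) = 0.0784. SE1 = √(0.096×0.904/44 + 0.276×0.724/66) = 0.0707. Then (0.18 − 1.96×0.0784)/0.0707 = 0.37, and power is 64.5%. The last column keeps 16% and 46% and multiplies the arm sizes by (1 − c).

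| c | Placebo | Active | Difference (points) | Odds ratio | Power, all men | Power, men able to improve |
|---|---|---|---|---|---|---|
| 0% | 16.0% | 46.0% | 30 | 4.47 | 92.6% | 92.6% |
| 10% | 14.4% | 41.4% | 27 | 4.20 | 87.9% | 89.6% |
| 20% | 12.8% | 36.8% | 24 | 3.97 | 81.7% | 85.6% |
| 30% | 11.2% | 32.2% | 21 | 3.77 | 73.8% | 80.3% |
| 40% | 9.6% | 27.6% | 18 | 3.59 | 64.5% | 73.4% |

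At c = 40% the loss is 92.6 − 64.5 = 28.1 points, of which 73.4 − 64.5 = 8.9 comes back by setting the ceiling men aside. The rest is lost because those men carry no information about treatment.

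**3. What the covariate alone does for endpoint 16.** Simulation, 44 versus 66, 3,000 trials per setting. Baseline categories 1 to 4 occur in ratio 2:3:3:2, plus a share c at 5. Response is 50% versus 25% at the centre of categories 1 to 4, with a logit slope of −0.4 per category and no response possible at 5. The model with treatment alone is compared with treatment plus baseline item score; baseline IELT and site were not simulated.
- c = 0: gain about 2 points.
- c = 10%: 64% to 69%.
- c = 30%: 49% to 57%.
- c = 40%: 39% to 51%.

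Restricting to baseline 4 or lower changes power by less than 1 point beyond this. The standard error of one simulated power is about √(0.5×0.5/3000) = 0.9 points, so the smallest gains are only approximate. If response does not depend on category within 1 to 4 (rates as in step 2; 2,000 trials), the covariate recovers less: at c = 40%, 61.4% without it, 68.1% with it, 72.2% in men able to improve.

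**4. Key endpoints.** Here only precision is at issue. With two baseline control categories and 40% versus 15% response at their midpoint on the logit scale, the gain from adding the category depends on the odds ratio between them:
- 1.5, 2 and 3: gains of 0.2, 0.3 and 1.7 points.
- 4: 77% to 81% in one set of simulated trials, 79% to 82% in another.
- 8: 71% to 78%, and 71% to 80%.

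**5. Chance imbalance.** The standard deviation of the between-arm difference in the share at category 5 is √(c(1−c)(1/44 + 1/66)): 7.8 points at c = 20%, 9.5 at c = 40%. This is noise, not bias.

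**The case against.** A reader might infer more than the documents support.

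- **That the secondary objective is undermined.** It is not. Endpoint 17 analyses the same items as change scores with baseline adjustment; endpoint 16 is a companion responder count among the other secondary endpoints.
- **That the missing covariate turns ceiling men into failures.** The endpoint definition does that. Adding the covariate leaves them non-responders; it only stops their presence from blurring the comparison.
- **That the ceiling reaches the key endpoints.** Exclusions 3 and 4 leave every man room to improve on control and distress. For PGIS, no PE at baseline is hardly compatible with entry.
- **That all three remaining items are unconstrained.** Inclusion 3 asks for negative consequences and names bother. Section 1.1 describes low satisfaction as common in PE, so many men at very good satisfaction is unlikely. Interpersonal difficulty is the item most exposed.
- **That the tests are invalid.** Randomisation keeps them valid, and chance imbalance is not bias.
- **That men able to improve should be the main population.** The share of all treated men who improve is a legitimate quantity, and section 7.6.2 specifies ITT. Restriction changes the question and, in the simulation with a baseline slope, adds almost nothing once the covariate is in.

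It is also fair that the ceiling share could be near zero, and that odds ratios of 4 to 8 between adjacent control categories have no support in the documents. What the objection does not answer is the omission itself: a predictor already collected, and already used for the same items one subsection earlier, is left out of the responder models.

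**Conclusion.** The point holds as a matter of efficiency and consistency, not of validity. The size for endpoint 16 rests on the undocumented ceiling share and on the assumed response pattern in step 3: about 2 points of power with no men at category 5, 5 at 10%, 8 at 30% and 12 at 40%. For the key endpoints it rests on how strongly baseline category predicts response: about 0 to 2 points at odds ratios of 1.5 to 3, and 4 to 8 points at 4 to 8. Most of the power lost to men at the ceiling cannot be recovered by any analysis.

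**What to change.** - In section 7.6.2.2 and the synopsis, add the baseline category of the analysed item as a factor in every PEP and PGIS logistic model (key secondary 4 to 6, other secondary 15 and 16). Use both the control and the distress baselines for endpoint 6.
- State the coding. On endpoint 16, category 5 as its own class level has no responders, so its coefficient does not converge. The treatment estimate then equals that of men with baseline 4 or lower. A numeric score avoids this.
- For endpoint 16, keep ITT as the main analysis, report the share at category 5 by arm, and add a supportive analysis in men with baseline 4 or lower on the item.

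**Cost.** No new data: PEP and PGIS are completed at Visit 2. The wording should be settled before unblinding. Editing section 7.6.2.2 and the synopsis is a protocol change, which under section 10.2 needs IRB approval. The supportive analysis has a smaller, item-specific denominator, but it is defined by a pre-treatment value, so the randomised comparison is preserved.
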